As well as scheduling and addressing appropriate anti-cancer treatments, such as chemotherapy or radiotherapy, lung cancer treatment planning needs to take into account many other factors, such as social factors, which should not cause further burden to the patient. One way of ensuring that these needs are met is to refer the patients to specialist palliative care (SPC) services which can identify and deal with these issues. Often SPC allows patients to focus on their important priorities with advance care planning, helping them to know when to pursue or withdraw from anti-cancer treatments and what level of medical interventions they would like at the end of life.

A recent trial carried out in a single hospital in USA by Temel and team (2010)^[3] showed that randomly allocating advanced NSCLC patients to standard care or earlier referral to palliative led to improved symptom control and psychological state in those having the palliative care, a reduced usage of invasive interventions including chemotherapy and attempts at resuscitation and, surprisingly, a longer survival. In the USA in general, palliative care is relatively under-developed and nearly always offered very near the end of their life.

Although SPC is much more developed in the UK and theoretically available to all who need it, regardless of nearness to death, in practice it varies because of local resources and also the knowledge and attitudes of cancer teams.

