2 AIMS, OBJECTIVES AND OUTCOME MEASURES

2.1 Aims and Objectives

The overall aim of the proposed research is to answer the question set by National Institute of Health Research Health (NIHR) Health Technology Assessment Programme (HTA), namely "What is the clinical and cost-effectiveness of introducing specialist palliative care soon after diagnosis on quality of life and end-of-life care among patients with metastatic non-small-cell lung cancer?"

This is a complex question in a very complex clinical and social scenario and therefore the trial addresses a number of specific research questions and objectives.

The specific objectives are set out here as a series of research questions:

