2.2.2 Randomised Controlled Trial Outcome Measures

The primary objective is to compare the two treatment arms in terms of the two co-primary outcome measures:

- (i) Global Health Status Score (GHSS) at three months post randomisation, and
- (ii) Quality-Adjusted Survival time (QAS) over six months

Secondary outcome measures:

- Overall survival
- Anxiety/depression
- Pain
- Quality of Life
- Cost-effectiveness
- Resource use
 - Days spent in hospital/hospice
 - Admission to an Intensive Therapy Unit (ITU)
 - Use of medical interventions in last month of life (see Appendix 1 for definitions)
 - Use of cardio-pulmonary resuscitation (CPR)
 - Compare the arms of SPARC sub-randomisation in the early palliative care group to see if HNA as an intervention is associated with better outcomes

The following will be measured from trial entry at each clinic visit the patient attends until the end of the trial or death:

- Health related quality of life using EQ-5D-5L and European Organisation for Research and Treatment of Cancer (EORTC) QLQ C30/LC13/BM22
- Hospital Anxiety and Depression Scale (HADS)
- HNA using SPARC (see Appendix 2)
- Modified Glasgow Prognostic Score (mGPS) (see Appendix 3)
- Nurse-rated and patient-rated ECOG
- Montreal Cognitive Assessment scale (MoCA) (see Appendix 4)

Additionally carers will receive:

- Short form-12® (SF-12®) health related quality of life questionnaire
- Family caregiver satisfaction of palliative care services questionnaire (FAMCARE-2)
- The CODE™ instrument

The modified Glasgow Prognostic Score will be used primarily as a prognostic and stratification measure at baseline. It will be repeated again at the key primary end-points of three months and six months to test for its utility as a prognostic score later in the disease ^{[7],[8]}.

In order to control for effects of co-morbidity on patients' physical condition and holistic needs, the Scottish Lung Cancer Co-Morbidity Index (see Appendix 5) will also be used at baseline^[9]. Neither this co-morbidity index nor the mGPS are outcome measures but do represent important potential antecedent variables which could influence symptoms and other holistic needs as well as survival, so will be used in the statistical analysis to help explain variations in the patients' outcomes.

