19.2.1.2 Secondary outcome measures

A secondary objective will be to compare the arms of SPARC sub-randomisation in the early palliative care group to see if HNA as an intervention is associated with better outcomes.

Other secondary outcome measures are defined as:

Overall survival: defined as the time from randomisation to death (due to any cause) or to date last seen for those not known to have died.

Anxiety/depression: will be measured using the HADS questionnaire and scored as per the HADS algorithm.

Pain: based on the EORTC QLQ-C30 and -LC13 questionnaire pain domains.

Health Economics; Cost Effectiveness and Resource Use

- Days spent in hospital/hospice: obtained from patient records. Duration defined as time from admission to discharge.
- Use, or not, of medical interventions in last month of life: details of further interventions administered during the last month of life will be obtained from patient records. The patient subgroup will be defined as those for which death was observed.
- **ITU admission:** the number of patients admitted, the frequency and duration of visits will be obtained from patient records. Duration is defined as the time from admission to discharge from intensive treatment unit.
- Use of CPR: obtained from patient records.

QoL: Health related quality of life will be assessed using EQ-5D-5L and EORTC QLQ C30/LC13/BM22 instruments. The instruments will be scored as per the associated algorithm.

Memory and cognitive ability: will be assessed for consenting participants using administration of the MoCA. The instruments will be scored as per the associated algorithm.

mGPS: will be assessed at baseline, 3 and 6 months. The instruments will be scored as per the associated algorithm.

Secondary outcomes pertaining to family care-givers include:

Health Survey: assessed using the SF-12®. The instruments will be scored as per the associated algorithm.

Satisfaction with participant's end of life care: assessed using the CODE™ instrument and scored as per the associated algorithms.

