19.2.2.2 Secondary Outcome Measures

The following measures will be reported by treatment arm:

Overall survival: A Kaplan Meier plot of overall survival will be reported along with hazard ratio and median survival (both with 95% CI).

Anxiety/depression: The average change in HADS score from baseline to six months will be compared using a t-test (or non-parametric alternative). The mean area under curve will also be compared using a t-test.

Pain: The average change in pain domain score from baseline to six months will be compared using a t-test (or non-parametric alternative). The mean area under curve will also be compared using a t-test.

Cost Effectiveness:

- Days spent in hospital/hospice Mean (95% CI) stay and overall stay duration and frequency
 of hospital/hospice say durations will be compared using a t-test (or non-parametric alternative).
 The number of patients admitted but not discharged will be reported. The proportion of patients
 spending time in hospital/hospice will be reported.
- Use, or not, of medical interventions in last month of life A line-listing of medical interventions including, where applicable, intervention type, dose, duration and other pertinent metrics. The period over which these interventions are to be observed will also be reported (some may not have been followed for a month).

ITU admission: The number of ITU visits, and the number of patients making those visits along with the mean (95% CI) length of each visit, and the mean (95% CI) of patients overall ITU duration.

Use of CPR: The proportion of patients requiring CPR and the average number of resuscitations required per patient will be reported.

For each of the questionnaire based outcome measures the mean (sd) score will be reported by visit.

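### Intervention use in the last month of life is defined as a yes/no outcome but will only be line-listed, so no between-arm estimate is planned for it

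*Protocol*

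**What the plan says.** - **Question.** Protocol section 2.1 gives the commissioned question as the effect of introducing specialist palliative care "soon after diagnosis on quality of life and end-of-life care among patients with metastatic non-small-cell lung cancer".
- **Precedent.** Section 1.1 reports that the earlier US trial found, among other benefits, "a reduced usage of invasive interventions including chemotherapy and attempts at resuscitation". Section 1.2 says this trial asks whether UK early referral achieves the same benefits.
- **Outcome.** Section 2.2.2 lists last-month intervention use as a secondary outcome and refers to Appendix 1 for its definition. Section 19.2.1.2 words it as "Use, or not, of medical interventions in last month of life" and sets the population: "The patient subgroup will be defined as those for which death was observed".
- **Analysis.** Section 19.2.2.2 names "A line-listing of medical interventions including, where applicable, intervention type, dose, duration and other pertinent metrics" and adds "The period over which these interventions are to be observed will also be reported", noting that some patients may have been followed for less than a month. It names nothing else for this outcome.
- **Data.** Section 7.2.4 requires a clinical records review after each death, covering the interventions received in the preceding month. Appendix 1 also has the last dose of chemotherapy, targeted therapy and radiotherapy dated relative to death.

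**The concern.** The definition and the analysis do not match. A use/no-use outcome in a stated population calls for a proportion in each arm and a contrast between arms; a listing supplies neither. Section 19.2.2 describes its contents as an outline, but for this outcome the outline is not silent. It names a method, and that method is weaker than those given to the neighbouring outcomes.

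At stake is whether the trial's planned results will say how far early referral changes treatment near death. Chemotherapy close to death is the clearest gap: sites collect the data, the US trial reported an effect, and the stated analysis offers only a listing.

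**Working it through.** **1. Analyses named in section 19.2.2.2, side by side**

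| Outcome | Planned output by arm | Limited to last month of life? |
|---|---|---|
| Overall survival | Kaplan-Meier, hazard ratio and median with 95% CI | Not applicable |
| Hospital/hospice days | Mean with 95% CI, t-test or non-parametric alternative, proportion with a stay | No |
| ITU admission | Patients and visits, mean durations with 95% CI | No |
| CPR | Proportion of patients, mean number of attempts | No |
| CODE | Covered by the general mean (SD) line for questionnaires | Last days, but a carer rating of care |
| Interventions in last month of life | Line-listing and period observed | Yes |

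The last row is the only one without a summary statistic. CPR overlaps with it, because resuscitation attempts are an Appendix 1 item. Anti-cancer drug treatment, radiotherapy and the other Appendix 1 items have no planned proportion.

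**2. Could an estimate be informative?**

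The protocol gives no precision or power figure for this outcome. Its general sample size does reproduce: for the Global Health Status Score, a 7-point difference, SD 23, 5% two-sided and 80% power give 342 analysed by the t-distribution. With 35% loss, 342/0.65 = 526, against 525 stated.

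Inputs from the protocol:
- exponential survival, median six months (19.2.5.1), so λ = ln 2/6 = 0.1155 per month
- three-year accrual (3.2)
- analysis after the last patient's six-month visit (19.2.4)
- 1:1 allocation (6.2)
- N = 525 (19.2.5)

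Assumptions not in the protocol: uniform accrual, equal survival in both arms, and the usage rate p.

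Expected proportion dead at analysis, with follow-up uniform between 6 and 42 months:

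1 − (e^(−6λ) − e^(−42λ))/(36λ) = 1 − (0.5 − 0.0078)/4.159 = 0.882

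Deaths: 525 × 0.882 ≈ 463, about 231 per arm. Counting only deaths within six months of randomisation, 525 × 0.5/2 ≈ 131 per arm.

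95% CI half-width for the risk difference = 1.96 × √(2p(1−p)/n):

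| Assumed p | n = 231 per arm | n = 131 per arm |
|---|---|---|
| 10% | 5.5 points | 7.3 points |
| 30% | 8.3 points | 11.1 points |
| 50% | 9.1 points | 12.1 points |

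The reduction detectable with 80% power (5% two-sided) is about 11 points from 30% and 13 points from 50% with 231 per arm. With 131 per arm it is about 14.5 and 17 points.

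These figures show that an estimate is feasible and reasonably precise. They do not measure an error in the plan.

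**The case against.** **The protocol text is only an outline.** Section 19.2.2 defers full detail to a statistical analysis plan, which may add a summary table. Nothing says that the listing excludes one. This stands in part. A reader might infer that any later comparison must be post hoc, with a free choice of definitions. The documents do not support that: a comparison fixed in the analysis plan before the data are analysed would be pre-specified, and the protocol already fixes the window, the population, the use/no-use form and the list of interventions. But the protocol names a method here, and it does not suit the outcome as defined.

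**Other end-of-life results are reported by arm.** This also stands. A reader might infer that the trial gives no between-arm result at all on the end-of-life part of its commissioned question. That is too strong: CPR, ITU use, hospital/hospice days and CODE all fall under the by-arm heading, and hospital/hospice days are formally compared. They do not fill this gap, however. The first three are not confined to the last month, and CODE rates care and does not count interventions.

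**A complete listing by arm contains every count.** True; no data are lost. What is missing is a stated summary.

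**An estimate among deceased patients has its own weaknesses.** It conditions on a post-randomisation event that early referral may itself affect, and pooling all of Appendix 1 mixes palliative sedation and antibiotics for symptom relief with chemotherapy and resuscitation. Both points stand and shape the remedy.

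**Conclusion.** The point holds for this one secondary outcome: section 19.2.2.2 plans no between-arm estimate of intervention use in the last month of life, although section 19.2.1.2 defines it as a yes/no measure. It does not extend to end-of-life care as a whole, and the co-primary outcomes and the sample size are unaffected.

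Too few deaths would not justify stopping at a listing. With about 231 deaths per arm, the CI half-width is about 5.5 to 9 points for usage rates of 10% to 50%; with about 131 per arm it is about 7 to 12 points. These ranges rest on the protocol's exponential six-month median and on assumed uniform accrual, equal survival and usage rates. The change is worth making because the outcome bears on the funder's question and on a benefit that the trial sets out to test.

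**What to change.** In section 19.2.2.2, replace the listing as the main output with a table by arm among deceased patients:

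- Give the number and percentage receiving each main Appendix 1 type in the last month of life: anti-cancer drug treatment, radiotherapy, resuscitation attempt, other interventional technologies, and end-of-life measures.
- For each, give the A versus B risk difference with 95% CI.
- Label these estimates as conditional on death, and read them beside the survival result.
- Treat any composite of all interventions as supplementary, since it has no clear direction of benefit.
- State how patients observed for less than a month are handled, with a sensitivity analysis restricted to those observed for the full month.
- Keep the listing as a supplement.

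The cost is one extra table from data already collected and a few more secondary estimates. It needs no extra patients, visits or procedures.

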19.2.3 Planned Sub Group Analyses

No subgroup analyses are planned at present. The TMG and DMC will review the trial data and developments in treatment of this patient population and the protocol will be updated accordingly with details of subgroups of interest.

19.2.4 Planned Final Analyses

The planned final analysis will be determined once the feasibility study has been completed and the trial office is in receipt of all data to conduct such analysis. The DMC will inform of the result at the RCT stage.

The planned final analyses will be conducted for the RCT stage once all data pertaining to the last patients' visit six months after randomisation has been completed. The analysis of outcomes will be carried out once the data has been captured.

19.2.5 Sample Size Justification

The trial will recruit, at a minimum, a total of 525 patients to ensure 80% power for both primary outcome measures but if our recruitment rate allows then we will aim to recruit more patients within the recruitment period to improve the power, to a maximum of 700 patients for 90% power. The rationale behind these sample sizes is given below.

19.2.5.1 Global Health Status Score

Assuming a median survival time in these patients of six months and an exponential distribution, it is expected that 70% of randomised patients will be alive at three months. Experience in the BTOG2 trial shows that we would expect high compliance in these remaining patients, so we assume a further 5% dropout for reasons other than death, giving a total loss of 35% of randomised patients. From literature, GHSS in patients with metastatic NSCLC is 58.8 with standard deviation of 23 points and data from the stage IV patients in the BTOG2 trial shows similar values with a mean GHSS at baseline of 61.5 and standard deviation (SD) of 23. A difference of seven points between treatment groups at three months, which is a standardised effect size of 0.3, is considered to be realistic and clinically relevant. Assuming a 5% two-sided significance level and 80% power the analysis requires a total of 342 patients to detect this level of difference and thus 525 randomised patients. For 90% power the analysis requires a total of 456 patients and thus 700 randomised patients.

19.2.5.2 Quality adjusted survival

Assuming a standard deviation of two (which is a reasonable assumption given the likely range of values) and two-sided significance level of 5%, the trial needs 506 patients in the analysis to have 80% power to detect a difference of 0.5 of a quality-adjusted life month between the treatment groups. For 90% power 676 patients would be required. Since this analysis includes all patients in an intention-to-treat analysis, this represents the required number of randomised patients.

Page | 34 of 64 Version 1.0a, 8 Apr 2016

20 TRIAL ORGANISATIONAL STRUCTURE

20.1 Sponsor

The trial will be run by the University of Sheffield, in collaboration with Sheffield Teaching Hospitals NHS Foundation Trust who will act as governance sponsor.

20.2 Co-ordinating Centre

The trial is being conducted under the auspices of the CRCTU, University of Birmingham according to their local procedures.

20.3 Trial Management Group

The Chief Investigator, Co-investigators including the Trial Statistician, Trial Manager and Trial Coordinator will form the TMG. The TMG will be responsible for the day-to-day conduct of the trial, meeting at regular intervals (e.g. every 3 months), or as required, usually be teleconference. They will be responsible for the set-up, promotion, on-going management of the trial, the interpretation of the results and preparation and presentation of relevant publications.

20.4 Trial Steering Committee

An independent TSC has been set up to oversee the trial. Membership will be composed of selected TMG members, representatives from the funders and at least one patient advocate. The TSC will meet shortly before commencement of the trial and annually (usually by teleconference), they will supervise the conduct of the trial, monitoring progress including recruitment, data completeness, losses to follow-up, and deviations from the protocol. They will make recommendations about conduct and continuation of the trial.

20.5 Data Monitoring Committee

Data analyses will be supplied in confidence to an independent DMC, which will be asked to give advice on whether the accumulated data from the trial, together with the results from other relevant research, justifies the continuing recruitment of further patients. The DMC will operate in accordance with a trial specific charter based upon the template created by the Damocles Group.

The DMC will meet at the end of the feasibility study and make recommendations to the HTA via the TSC regarding the viability of the RCT. Specific progression criteria from the feasibility study to the RCT are outlined in Section 19.1.1.

The DMC is then scheduled to meet six months after the RCT opens to recruitment and then annually until last patient is recruited. Additional meetings may be called if recruitment is much faster than anticipated and the DMC may, at their discretion, request to meet more frequently or continue to meet following completion of recruitment. An emergency meeting may also be convened if a safety issue is identified. The DMC will report directly to the TSC via the Trial Office. The TSC will consider the DMCs findings and make recommendations to the TMG, HTA and sponsor. The DMC may consider recommending the discontinuation of the trial if the recruitment rate or data quality are unacceptable or if any issues are identified which may compromise patient safety.

Page | 35 of 64 Version 1.0a, 8 Apr 2016

21 FINANCE

This is an investigator-initiated and investigator-led trial funded by the NIHR HTA programme.

The sponsor will pay research costs, as defined in the Clinical Site Agreement, to participating sites.

The trial has been adopted by the NIHR Cancer Research Network Portfolio.

22 ETHICAL CONSIDERATIONS

The trial will be performed in accordance with the recommendations guiding physicians in biomedical research involving human subjects, adopted by the 18th World Medical Association (WMA) General Assembly, Helsinki, Finland, 1964, amended by the 48th WMA General Assembly, Somerset West, Republic of South Africa, 1996 (website: http://www.wma.net/en/30publications/10policies/b3/index.html) (Appendix 12).

The trial will be conducted in accordance with the Research Governance Framework for Health and Social Care, the applicable UK Statutory Instruments, (which include the Data Protection Act 1998 and GCP. The protocol will be submitted to and approved by the REC prior to circulation.

Before any patients are enrolled into the trial, the Principal Investigator at each site is required to obtain local R&D approval. Sites will not be permitted to enrol patients until written confirmation of R&D approval is received by the Trial Office.

It is the responsibility of the Principal Investigator to ensure that all subsequent amendments gain the necessary local approval. This does not affect the individual clinicians' responsibility to take immediate action if thought necessary to protect the health and interest of individual patients.

23 CONFIDENTIALITY AND DATA PROTECTION

Personal data recorded on all documents will be regarded as strictly confidential and will be handled and stored in accordance with the Data Protection Act 1998.

Full name and telephone number will be collected at trial entry for those patients and carers agreeing to participate in the Qualitative Interviews. This information will be shared via a secure method with the Qualitative Researchers in Sheffield. At the end of the study this information will be deleted from the trial database. If the patient or carer wishes to be interviewed at home the patient will also need to notify the Qualitative Researcher of their address. The interviews will be recorded by the Qualitative Researchers. These tapes will be transcribed and the transcriptions anonymised.

Initials date of birth, and hospital number will be collected for all patients and initials will also be collected for consenting carers. Patients will be identified using only their unique identifier, initials and date of birth on the CRF and correspondence between the Trial Office and the participating site. However patients and carers are asked to give permission for the Trial Office to be sent a copy of their signed Informed Consent Form(s) which will not be anonymised. This will be used to perform in-house monitoring of the consent process.

Page | 36 of 64 Version 1.0a, 8 Apr 2016

The investigator must maintain documents not for submission to the Trial Office (e.g. Patient Identification Logs) in strict confidence. In the case of specific issues and/or queries from the regulatory authorities, it will be necessary to have access to the complete trial records, provided that patient confidentiality is protected.

The Trial Office will maintain the confidentiality of all patients' and carers' data and will not disclose information by which these individuals may be identified to any third party. Representatives of the SPECIAL trial team may be required to have access to patient's medical records for quality assurance purposes but patients should be reassured that their confidentiality will be respected at all times.

